4.6.2.5. Depression

Depression will be defined using terms from the Depression and suicide/self injury SMQ.

The frequency and percentage of patients with treatment-emergent depression will be summarized by treatment arm, maximum severity, SOC, and Preferred Term during the Treatment Period. Exposure-adjusted incidence rates (per 100 patient years), as defined in Section 6.14.2.1, for each type of treatment-emergent depression will be presented by treatment arm, Preferred Term and time interval during the Treatment Period. Adverse events will be summarized under a particular time interval if they started or worsened on or after the interval start date and before the interval end date. Exposure-adjusted incidence rates will also be presented graphically by treatment arm and time interval.

A by-patient listing of treatment-emergent depression will be provided.

4.6.2.6. Suicide-related Thoughts and Behaviors

Suicide-related ideations and behaviors, based on C-SSRS, will be summarized by treatment arm separately for patients who completed the C-SSRS starting at enrollment versus patients who were already enrolled when the C-SSRS was introduced to the study during the Treatment Period.

Treatment-emergent suicide-related ideations and behaviors during the Treatment Period are defined as any ideation or behavior reported after the baseline visit (Visit 2) and on or prior to Visit 10 (Week 24) or early discontinuation. The frequency and percentage of patients with treatment-emergent suicide-related ideations and behaviors will be summarized by treatment arm for patients who completed the C-SSRS starting at enrollment by C-SSRS category (1-10), by type (ideation or behavior) and overall during the Treatment Period.

Suicide-related ideations and behaviors will be listed by patient and visit separately for patients who completed the C-SSRS starting at enrollment versus patients who were already enrolled when the C-SSRS was introduced to the study. Only patients that show suicidal ideation/behavior will be displayed, including lifetime history at screening. If a patient answers are all 'no' for the C-SSRS, then that patient will not be displayed. However, if a patient reported any ideation or

behavior at any time point then all their ideation and behavior will be displayed, even if not positive.

4.6.3. Clinical Laboratory Evaluation

All numerical laboratory tests for serum chemistries, fasting lipids, hematology, RF and anti-CCP antibodies, CRP, and ESR will be summarized by treatment arm for baseline, all post-baseline visits during the Treatment Period, Week 24 endpoint, and change from baseline to post-baseline visits and Week 24 endpoint.

Urinalysis, TSH, and T4 are collected at screening only, and will appear in data listings.

Summary of B-cells, immunoglobulins, immunogenicity tests, and BAFF levels are described in the subsections below.

Change from baseline to Week 24 endpoint in laboratory tests will be summarized for patients who have both a baseline and at least one post-baseline result. For all laboratory tests except CD3-CD20+B cells counts, baseline is defined as the last non-missing result on or prior to the date of the first injection of study treatment.

Change from the minimum value on or prior to the date of the first injection of study treatment to the minimum value during the Treatment Period in laboratory tests will be summarized for patients who have both a baseline and at least one post-baseline result. Similarly, change from the maximum value on or prior to the date of the first injection of study treatment to the maximum value during the Treatment Period in laboratory tests will be summarized for patients who have both a baseline and at least one post-baseline result. Scheduled visits, unscheduled visits, and repeat measurements will be included.

The frequency and percentage of patients with treatment-emergent abnormal, high, or low laboratory results at any time will be summarized. Similarly, the frequency and percentage of patients with treatment-emergent abnormal, high, or low laboratory results at Week 24 endpoint will be summarized. A treatment-emergent abnormal result is defined as a change from normal at all baseline visits to abnormal at any time during the Treatment Period. A treatment-emergent high result is defined as a change from a value less than or equal to the high limit at all baseline visits to a value greater than the high limit at any time during the Treatment Period. A treatment-emergent low result is defined as a change from a value greater than or equal to the low limit at all baseline visits to a value less than the low limit at any time during the Treatment Period. For each laboratory test, only patients who were normal (i.e., less than or equal to the high limit for treatment-emergent high, or greater than or equal to the low limit for treatment-emergent low) at all baseline visits and who have at least one non-missing post-baseline result will be included in the denominator when computing the percentages of patients with treatment-emergent abnormal, high, or low results. Scheduled visits, unscheduled visits, and repeat measurements will be included. Covance Reference Ranges will be used to define the low and high limits.

Shifts from baseline to maximum post-baseline result during the Treatment Period for ALT, AST, and total bilirubin will be provided for the following categories:

- ALT; $\leq 1 \times \text{ULN}$, $> 1 \text{ to } \leq 3 \times \text{ULN}$, $> 3 \text{ to } \leq 5 \times \text{ULN}$, $> 5 \text{ to } \leq 10 \times \text{ULN}$, and $> 10 \times \text{ULN}$.

- AST; $\leq 1 \times \text{ULN}$, > 1 to $\leq 3 \times \text{ULN}$, > 3 to $\leq 5 \times \text{ULN}$, > 5 to $\leq 10 \times \text{ULN}$, and $> 10 \times \text{ULN}$.
- Total bilirubin; $\leq 1 \times \text{ULN}$, > 1 to $\leq 1.5 \times \text{ULN}$, $> 1.5 \times \text{ULN}$.

Shifts from baseline to minimum post-baseline result during the Treatment Period for neutrophils, lymphocytes, and leukocytes will be provided for the following categories:

- Neutrophils; $< \text{LLN}$ to $\geq 1.5 \times 10^9/\text{L}$, $< 1.5 \times 10^9/\text{L}$ to $\geq 1.0 \times 10^9/\text{L}$, $< 1.0 \times 10^9/\text{L}$ to $\geq 0.5 \times 10^9/\text{L}$, and $< 0.5 \times 10^9/\text{L}$.
- Leukocytes; $< \text{LLN}$ to $\geq 3.0 \times 10^9/\text{L}$, $< 3.0 \times 10^9/\text{L}$ to $\geq 2.0 \times 10^9/\text{L}$, $< 2.0 \times 10^9/\text{L}$ to $\geq 1.0 \times 10^9/\text{L}$, and $< 1.0 \times 10^9/\text{L}$.
- Lymphocytes; $< \text{LLN}$ to $\geq 0.8 \times 10^9/\text{L}$, $< 0.8 \times 10^9/\text{L}$ to $\geq 0.5 \times 10^9/\text{L}$, $< 0.5 \times 10^9/\text{L}$ to $\geq 0.2 \times 10^9/\text{L}$, and $< 0.2 \times 10^9/\text{L}$.

Scheduled visits, unscheduled visits, and repeat measurements will be included.

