Clinician-Administered Tender/Swollen Joint Count (TSJC) (68/66)	X	X	X	X	X	X	X	X	X	X	X	X	X	Collected via an electronic tablet device. These joint counts will be performed by the Joint Assessor (Section 6.3). Determine prior to dosing
Physician's Global Assessment of Disease Activity (PhGADA_VAS)	X	X	X	X	X	X	X	X	X	X	X	X	X	Determine prior to dosing
Clinician-Administered Assessments (Paper)														
C-SSRS Screening/Baseline	X													Administer before any clinical assessments and dosing
C-SSRS Since Last Assessed		X	X	X	X	X	X	X	X	X	X	X	X	Administer before any clinical assessments and dosing
Self-harm Supplement Form	X	X	X	X	X	X	X	X	X	X	X	X	X	
Self-Harm Follow-Up Form	X	X	X	X	X	X	X	X	X	X	X	X	X	
Laboratory Tests and Sample Collections														
Hematology	X	X		X	X	X	X	X	X	X	X	X	X	Collect prior to dosing
Clinical Chemistry	X	X		X	X	X	X	X	X	X	X	X	X	In addition to scheduled assessments, these laboratory tests may also be performed as clinically indicated. Collect prior to dosing.

Study J1A-MC-KDAD	Screen	Period 1: Double-blind treatment					Period 2				ED	Post-treatment follow-up		Comments
Day ± Visit Tolerance	-42 to -1	1	14 ± 7	28 ± 7	56 ± 7	84 ± 7	98 ± 7	112 ± 7	140 ± 7	168 ± 7	Any	196 ± 7	252 ± 7	Visit 1 procedures may be conducted over more than 1 day as long as all tasks are completed within the tolerance window.
Week	-	2	4	8	12	14	16	20	24	-	28	36 or ETV + 12		
Visit number	V1	V2	V3	V4	V5	V6	V7	V8	V9	V10	ET	V801	V802	
Procedures														
Urinalysis	X	X			X			X		X	X		X	In addition to scheduled assessments, these laboratory tests may also be performed as clinically indicated. Collect prior to dosing.
Serum pregnancy	X													For all women of childbearing potential (Section 10.4).
Urine pregnancy (local)		X		X	X	X		X	X	X	X	X	X	Determine results prior to dosing
Follicle Stimulating Hormone (FSH)	X													For women who are considered postmenopausal to confirm postmenopausal status.
C-Reactive Protein, high-sensitivity (hsCRP)	X	X	X	X	X	X	X	X	X	X	X	X	X	Collect prior to dosing
Erythrocyte sedimentation rate (ESR)	X	X				X				X	X	X	X	Collect prior to dosing
Rheumatoid factor (RF)	X	X				X				X	X	X	X	Collect prior to dosing
Anticyclic citrullinated peptide (anti-CCP)	X	X				X				X	X	X	X	Collect prior to dosing
Soluble PD-1		X	X	X	X	X		X		X	X	X	X	Collect prior to dosing
Soluble PD-L1		X	X	X	X	X		X		X	X	X	X	Collect prior to dosing.

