8.2.4. Clinical Safety Laboratory Assessments

See Section 10.2, Appendix 2 for the list of clinical laboratory tests to be performed and to the SoA for the timing and frequency.

The investigator must review the laboratory report, document this review, and record any clinically relevant changes occurring during the study in the AE section of the CRF. The

laboratory reports must be filed with the source documents. Clinically significant abnormal laboratory findings are those that are not associated with the underlying disease, unless judged by the investigator to be more severe than expected for the participant's condition.

All laboratory tests with values considered clinically significantly abnormal during participation in the study or within approximately 30 days after the last dose of study intervention should be repeated until the values return to normal or baseline or are no longer considered clinically significant by the investigator or medical monitor.

If such values do not return to normal/baseline within a period of time judged reasonable by the investigator, the etiology should be identified and the sponsor notified.

All protocol-required laboratory assessments, as defined in Section [10.2](#), Appendix 2, must be conducted in accordance with the laboratory manual and the SoA.

If laboratory values from nonprotocol specified laboratory assessments performed at the institution's local laboratory require a change in participant management or are considered clinically significant by the investigator (e.g., SAE or AE or dose modification), then these would be reported in the AE section of the CRF.

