9.4.7. Other Safety Analyses

Analyses/measures	Presented...
Safety analyses: AEs, SAEs, C-SSRS, vital signs, ECGs, and laboratory analytes	Descriptively summarized by treatment group, will use the safety population data
Categorical safety measures	Summarized with counts by visit
Continuous safety measures	Summarized as mean change by visit
Exposure to study intervention	Calculated for each participant and summarized by treatment group by treatment period

Adverse events

Adverse events will be coded according to the Medical Dictionary for Regulatory Activities (MedDRA) and summarized by system organ class, preferred term, severity, and relationship to the study intervention. All AEs, including pre-existing conditions, will be listed by participant, visit, preferred term, treatment group, severity, and relationship to the treatment.

Treatment-emergent adverse events

A TEAE is defined as an event that first occurred or worsened in severity after baseline, with baseline defined as all pre-existing conditions recorded at Visit 1 and any AEs recorded before the first dose of study intervention (that is, during the interval between Visits 1 and 2 and recorded with the time of onset before the first dose of study intervention). For events that are gender specific, the denominator and computation of the percentage will include only participants from the given gender.

The number and percentage of participants who experienced TEAEs, TEAEs by maximum severity, deaths, SAEs, TEAEs related to study intervention, discontinuations from the treatment due to an AE, and AESIs will be summarized. Treatment-emergent adverse events (all, by maximum severity), SAEs including deaths, and AEs that lead to treatment discontinuation will be summarized and analyzed by MedDRA system organ class and preferred term.

Treatment-related TEAEs (TEAEs related to study intervention) are defined as events that are indicated by the investigator on the eCRF to be related to treatment.

Adverse events of special interest will be identified by a standardized MedDRA query or a Lilly-defined MedDRA preferred term listing.

Suicide-related thoughts and behaviors

Suicide-related thoughts and behaviors occurring during treatment will be summarized based on responses to the C-SSRS consistent with the C-SSRS Scoring and Data Analysis Guide (Columbia Lighthouse Project WWW).

Follow-up emergent adverse events

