10.2. Appendix 2: Clinical Laboratory Tests

The tests detailed below will be performed by the central laboratory or by the local laboratory as specified in the table.

If the local laboratory results are used to make either a study intervention decision or response evaluation, the results must be entered into the CRF.

Protocol-specific requirements for inclusion or exclusion of participants are detailed in Section [5](#) of the protocol.

Additional tests may be performed at any time during the study as determined necessary by the investigator or required by local regulations.

Pregnancy testing will be performed according to the SoA (Section [1.3](#)).

Laboratory results that could unblind the study will not be reported to investigative sites or other blinded personnel.

Refer to Section [10.6](#), Appendix 6 for recommended laboratory testing for hypersensitivity events.

Clinical Laboratory Tests	Comments
Hematology	Assayed by Lilly-designated laboratory
Hemoglobin	
Hematocrit	
Erythrocyte count (RBCs - Red Blood Cells)	
Mean cell volume	
Mean cell hemoglobin	
Mean cell hemoglobin concentration	
Leukocytes (WBCs - White Blood Cells)	
Differential	
Neutrophils, segmented	
Lymphocytes	
Monocytes	
Eosinophils	
Basophils	
Platelets	
Cell Morphology (RBC and WBC)	
Clinical Chemistry	Assayed by Lilly-designated laboratory
Sodium	
Potassium	
Chloride	
Bicarbonate	
Total bilirubin	
Direct bilirubin	
Alkaline phosphatase (ALP)	
Alanine aminotransferase (ALT)	

Clinical Laboratory Tests	Comments
Aspartate aminotransferase (AST)	
Gamma-glutamyl transferase (GGT)	
Blood urea nitrogen (BUN)	
Creatinine	
Creatine kinase (CK)	
Uric acid	
Total protein	
Glomerular filtration rate (GFR)	Only performed at screening
Albumin	
Calcium	
Phosphorus	
Glucose	
Cholesterol	
Triglycerides	
Urinalysis	Assayed by Lilly-designated laboratory
Specific gravity	
pH	
Protein	
Glucose	
Ketones	
Bilirubin	
Urobilinogen	
Blood	
Nitrite	
Urine leukocyte esterase	
Microscopic examination of sediment	
Hormones (female)	
Serum Pregnancy	Assayed by Lilly-designated laboratory
Urine Pregnancy	Evaluated locally
Follicle stimulating hormone (FSH)	Assayed by Lilly-designated laboratory. Optional, performed as needed to confirm participant's postmenopausal status.
Serology	Assayed by Lilly-designated laboratory
Tuberculosis (TB) testing	See the protocol (Section 8.2.6) for more information about TB testing.

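### SAP 4.6.3 calls urinalysis screening-only and specifies no summary by arm, although the protocol also schedules it after dosing

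*SAP*

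**What the plan says.** SAP 4.6.3 opens with the laboratory groups that get by-visit summaries: "All numerical laboratory tests for serum chemistries, fasting lipids, hematology, RF and anti-CCP antibodies, CRP, and ESR will be summarized by treatment arm". Urinalysis is not among them. The SAP then says: "Urinalysis, TSH, and T4 are collected at screening only, and will appear in data listings". Later in the section it plans frequencies of treatment-emergent abnormal, high or low laboratory results, without naming any panel.

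The protocol says something different about timing. With blank cells dropped, the SoA row reads "Urinalysis X X X X X X X", which is seven marked visits. For laboratory safety tests, protocol 8.2.4 refers to Appendix 2 "for the list of clinical laboratory tests to be performed and to the SoA for the timing and frequency". Appendix 2 lists an 11-item urinalysis panel with no restriction on timing. It does mark one test, glomerular filtration rate, as "Only performed at screening".

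On reporting, protocol 9.4.7 has a row for "Safety analyses: AEs, SAEs, C-SSRS, vital signs, ECGs, and laboratory analytes", and the planned presentation is "Descriptively summarized by treatment group, will use the safety population data". The same table has categorical safety measures counted at each visit. Protocol 9.4.1 requires changes to the protocol's analysis methods to be described and justified in the SAP and the clinical study report. SAP 4.9 reports none.

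**The concern.** The SAP gives a factual reason for not summarising urinalysis, namely that nothing is collected after screening, and the SoA contradicts it. A programmer working from SAP 4.6.3 would produce a listing and no urinalysis table. Post-dose urine results would be collected from participants in all three arms without the summary by treatment group that the protocol plans, and no change would have been declared.

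At stake is one descriptive safety output: whether urine abnormalities such as protein or blood, when not reported as adverse events, are more frequent on LY3462817 than on placebo. Scattered low-grade findings are hard to compare across arms by reading a listing of about 80 participants randomised 2:1:1. A table of counts does it directly.

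**Working it through.** No sample size, power or error rate enters this point. The check sets the SoA row against the SAP sentence and then traces where urine results could be reported.

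**Step 1. Read the SoA row.** The urinalysis row has 13 visit cells, matching the 13 visits V1 to V10, ET, V801 and V802.

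| Visit | Time | Urinalysis | Relation to treatment |
|---|---|---|---|
| V1 | Screening | X | Before dosing |
| V2 | Baseline | X | Before first dose |
| V3, V4 | Weeks 2, 4 | none | Period 1 |
| V5 | Week 8 | X | Period 1, post-dose |
| V6 | Week 12 | none | End of Period 1 |
| V7 | Week 14 | none | Period 2 |
| V8 | Week 16 | X | Period 2 |
| V9 | Week 20 | none | Period 2 |
| V10 | Week 24 | X | Period 2 |
| ET | Any | X | Early termination |
| V801 | Week 28 | none | Follow-up |
| V802 | Week 36 or ET + 12 weeks | X | Follow-up, post-treatment |

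**Step 2. Count.**
- Marked visits: 7 of 13.
- After screening: 7 − 1 = 6.
- After the first dose: 6 − 1 (baseline) = 5, namely Weeks 8, 16 and 24 (three), ET (one) and V802 (one).
- Scheduled and post-dose within the 12-week placebo-controlled period: 1, at Week 8.

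A table read from PDF can shift columns, but no shift turns seven marks into a single screening collection. The row's comment ends "these laboratory tests may also be performed as clinically indicated. Collect prior to dosing". The clinical chemistry row carries the same comment, so it does not prove timing, but an instruction about dosing would be odd for a test done only at screening.

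**Step 3. Trace the reporting routes for a post-dose urine result.**
- By-visit laboratory summaries (SAP 4.6.3, opening list): urinalysis is not named.
- Treatment-emergent abnormal results (SAP 4.6.3, later paragraph): generic, so urinalysis is neither named nor excluded. SAP 4.1 defines the Treatment Period as Periods 1 and 2 together, so an at-any-time count would pool Week 8 with Weeks 16 and 24.
- Listing (SAP 4.6.3): yes.
- Adverse event tables (SAP 4.6.2): yes, if the result is judged clinically significant. Protocol 8.2.4 sends clinically relevant laboratory changes to the adverse event form, and the definition in protocol 10.3.1 names urinalysis.

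**Step 4. Place the samples.** Under protocol 4.1 and 6.5.3, all placebo participants, and LY3462817 participants without low disease activity at Week 14, stop infusions and should move to standard of care. Only LY3462817 participants with low disease activity remain on study drug at Weeks 16 and 24. SAP 1.2 instead says that all participants receive LY3462817 in Period 2. The two descriptions must be reconciled. On neither account is anyone still receiving placebo at those weeks. Apart from early termination samples, the randomised comparison therefore rests on Week 8: one scheduled sample per participant, in about 40 + 20 + 20 = 80 people.

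**Step 5. The other tests named.** TSH and T4 appear in neither the SoA nor Appendix 2. SAP 4.6.3 also says BAFF levels are described in later subsections, but none of them names BAFF, and nor does the protocol. Appendix 2 lists a cytokine panel without naming its analytes.

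**The case against.** The best defence is that the SAP does not exclude urinalysis. It says results will be listed, not that they will only be listed. Its by-visit sentence covers numerical tests, and the later provision defines abnormal separately from high and low, a category that suits qualitative urine results. On that reading, post-dose urine data fall under the treatment-emergent abnormal table. This stands as far as showing ambiguity, and so one cannot say flatly that urinalysis is excluded. It does not cure the problem. The specific sentence assumes no post-screening urine data exist, and even the generous reading gives neither counts by visit nor a separate Period 1 result.

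A reader might also infer that a urinary safety signal would be visible only in patient listings. The documents do not support that. Clinically significant urine findings are reported as adverse events and tabulated by arm, and serum creatinine and urea nitrogen are in the chemistry panel, which is summarised by arm.

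Nor are all five post-dose collections lost on-treatment comparisons: V802 is post-treatment, and Weeks 16 and 24 offer no comparison with participants still on placebo.

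Finally, a reader might conclude that the study does not collect BAFF. With the cytokine panel unspecified, that cannot be shown. The documents show only that BAFF is not named in the protocol and that the promised SAP subsection is missing.

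**Conclusion.** The inconsistency is real and minor. The SAP's statement about urinalysis collection is wrong against the supplied protocol: six of the seven scheduled collection points come after screening, and five after the first dose. As a result, the SAP specifies no summary by arm of post-dose urinalysis and does not declare this as a change.

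The practical loss is the tabulation of urine abnormalities that are not reported as adverse events, chiefly the Week 8 comparison. The data are still collected and can be listed. The primary analysis, power and the monitoring of individual participants are unaffected.

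The conclusion assumes that the SoA in the supplied protocol governs. The SAP says it is based on the protocol dated 05AUG2020. The supplied text mentions a decision of 08 September 2020, so it is later, and the SoA of the August version was not available. Whether this was an error from the start or an update that was missed cannot be told. The mention of TSH and T4, which this study does not schedule, suggests text carried over from elsewhere, but that is inference and the point does not depend on it.

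**What to change.** Replace the sentence in SAP 4.6.3; simply deleting it would remove the only explicit commitment to list urinalysis. The new text should:

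- state the SoA schedule (screening, baseline, Weeks 8, 16 and 24, early termination, V802);
- keep the by-patient listing;
- add counts of urinalysis results by arm and visit, and treatment-emergent abnormal urinalysis by arm;
- present Period 1 separately from Weeks 16 and 24, when under the protocol placebo participants and LY3462817 participants without low disease activity are off study drug.

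In the same edit, remove TSH and T4, and confirm whether BAFF is collected. If it is, name it and supply the missing subsection; if not, drop the reference. If listing-only reporting of urinalysis is in fact intended, it should be declared and justified in SAP 4.9.

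The cost is SAP wording and one table, with no new data collection.

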Participants who are discontinued from intervention due to a hepatic event or liver test abnormality should have additional hepatic safety data collected via eCRF. The investigator should consult with the medical monitor to determine if discontinuation of the intervention for abnormal liver tests **should be** considered if a participant meets one of these conditions (see Section 10.7, Appendix 8):

- ALT or AST >8 times ULN
- ALT or AST >5 times ULN for more than 2 weeks
- ALT or AST >3 times ULN and TBL >2 times ULN or international normalized ratio (INR) >1.5
- ALT or AST >3 times ULN with the appearance of fatigue, nausea, vomiting, right upper-quadrant pain or tenderness, fever, rash, and/or eosinophilia (>5%)
- ALP >3 times ULN
- ALP >2.5 times ULN and TBL >2 times ULN, or
- ALP >2.5 times ULN with the appearance of fatigue, nausea, vomiting, right quadrant pain or tenderness, fever, rash, and/or eosinophilia (>5%)

See the SoA for data to be collected at the time of intervention discontinuation and follow-up and for any further evaluations that need to be completed.

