ALT or AST \geq 1.5x ULN	ALT or AST \geq 2x baseline with hepatic signs/symptoms*, or ALT or AST \geq 3x baseline
ALP \geq 1.5x ULN	ALP \geq 2x baseline
TBL \geq 1.5x ULN	TBL \geq 1.5x baseline (except for participants with Gilbert's syndrome)

Abbreviations: ALP = alkaline phosphatase; ALT = alanine aminotransferase; AST = aspartate aminotransferase; TBL = total bilirubin level; ULN = upper limit of normal.

* Hepatic signs/symptoms are severe fatigue, nausea, vomiting, right upper quadrant abdominal pain, fever, rash, and/or eosinophilia >5%.

At a minimum, this evaluation should include physical examination and a thorough medical history, as outlined above, as well as tests for prothrombin time-international normalized ratio; tests for viral hepatitis A, B, C, or E; tests for autoimmune hepatitis; and an abdominal imaging study (for example, ultrasound or computed tomography scan).

Based on the participant's history and initial results, further testing should be considered in consultation with the Lilly-designated medical monitor, including tests for hepatitis D virus, cytomegalovirus, Epstein-Barr virus, acetaminophen levels, acetaminophen protein adducts, urine toxicology screen, Wilson's disease, blood alcohol levels, urinary ethyl glucuronide, and serum phosphatidylethanol.

Based on the circumstances and the investigator's assessment of the participant's clinical condition, the investigator should consider referring the participant for a hepatologist or gastroenterologist consultation, magnetic resonance cholangiopancreatography, endoscopic retrograde cholangiopancreatography, cardiac echocardiogram, or a liver biopsy.

Additional hepatic data collection (hepatic safety CRF)

Additional hepatic safety data collection in hepatic safety CRFs should be performed in study participants who meet 1 or more of the following 5 conditions:

If a participant with baseline...	has the following elevations...
ALT <1.5 × ULN	ALT ≥5 × ULN on 2 or more consecutive blood tests
ALP <1.5 × ULN	ALP ≥2 × ULN on 2 or more consecutive blood tests
TBL <1.5 × ULN	TBL ≥2 × ULN, except for cases of known Gilbert's syndrome
ALT ≥1.5 × ULN	ALT ≥3 × baseline on 2 or more consecutive blood tests
ALP ≥1.5 × ULN	ALP ≥2 × baseline on 2 or more consecutive blood tests
TBL ≥1.5 × ULN	TBL ≥2 × baseline

Abbreviations: ALP = alkaline phosphatase; ALT = alanine aminotransferase; TBL = total bilirubin level; ULN = upper limit of normal.

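### SAP 4.6.3's liver categories do not match the laboratory thresholds in protocol 7.1.2, so once the upper cells are occupied the planned tables cannot count who met them

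*SAP*

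**What the plan says.** SAP 4.6.3 (Clinical Laboratory Evaluation) plans this liver table: "Shifts from baseline to maximum post-baseline result during the Treatment Period for ALT, AST, and total bilirubin will be provided for the following categories". The cuts for ALT and for AST are 1, 3, 5 and 10×ULN. Total bilirubin is cut at 1 and 1.5×ULN, so everything above 1.5×ULN forms one group. ALP is not in the table, and no test is crossed with another.

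Protocol 7.1.2 lists seven liver conditions under permanent discontinuation. Two of them combine laboratory tests. The first is "ALT or AST >3 times ULN and TBL >2 times ULN or international normalized ratio (INR) >1.5"; the second, which turns on ALP, is "ALP >2.5 times ULN and TBL >2 times ULN, or". The remaining five are either transaminase above 8×ULN, either one above 5×ULN lasting over 2 weeks, either one above 3×ULN accompanied by symptoms or eosinophilia, ALP above 3×ULN, and ALP above 2.5×ULN accompanied by symptoms or eosinophilia. Meeting one leads the investigator to consult the medical monitor on whether to discontinue; it does not stop treatment automatically.

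Protocol Appendix 7 (10.7) adds a separate data stream: "Additional hepatic safety data collection in hepatic safety CRFs should be performed" when set limits are reached, among them bilirubin of at least 2×ULN and ALP of at least 2×ULN on consecutive tests. The SAP does not mention these data.

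Elsewhere in SAP 4.6.3, all serum chemistries, and so ALP, receive summaries by arm and visit, and treatment-emergent high or low counts against the laboratory's reference range.

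**The concern.** The protocol names the liver values at which the team must think about stopping the drug. A reader of the study report will want to know how many participants per arm reached them. The SAP's categories come from a different grid, so the question may have no answer in the planned outputs.

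This matters more than usual here. At the cutoff of 02 September 2020 in protocol 2.2, multiple-dose exposure was 6 participants at 75 mg and 7 at 300 mg, 13 in all. Methotrexate and leflunomide are permitted (not required) as background therapy. Hepatic events are not among the adverse events of special interest in protocol 8.3.6, and SAP 4.6.2 defines no hepatic analysis. The laboratory tables therefore carry most of the liver reporting.

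**Working it through.** The plan gives no figure to reproduce on this point. The check is whether the planned table determines the count for each condition.

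**Inputs.** The category limits are from SAP 4.6.3 and the seven conditions from protocol 7.1.2. The third is read as ALT/AST above 3×ULN together with either bilirubin above 2×ULN or INR above 1.5.

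**Step 1: can the table tell two participants apart?** For each condition take two hypothetical participants with the same cells for maximum ALT, AST and bilirubin, one meeting the condition and one not. If such a pair exists, the cell count does not give the condition count. Values are multiples of ULN; tests not named are at 1.

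| Condition | Meets it | Does not | Shared SAP cell |
|---|---|---|---|
| 1. ALT/AST >8 | ALT 9 | ALT 6 | ALT >5 to ≤10 |
| 2. ALT/AST >5 for over 2 weeks | ALT 6 on days 28 and 56 | ALT 6 on day 28, 1 on day 56 | ALT >5 to ≤10 |
| 3. ALT/AST >3 with bilirubin >2 or INR >1.5 | ALT 4, bilirubin 2.5 | ALT 4, bilirubin 1.8 | ALT >3 to ≤5; bilirubin >1.5 |
| 4. ALT/AST >3 with symptoms or eosinophilia | ALT 4, symptoms | ALT 4, none | ALT >3 to ≤5 |
| 5. ALP >3 | ALP 3.5 | ALP 1 | no ALP cell |
| 6. ALP >2.5 with bilirubin >2 | ALP 2.7, bilirubin 2.5 | ALP 1, bilirubin 2.5 | bilirubin >1.5 |
| 7. ALP >2.5 with symptoms or eosinophilia | ALP 2.7, symptoms | ALP 1, symptoms | no ALP cell |

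A pair exists for all seven. Counting each condition once by its main obstacle: one lacks the 8×ULN cut, one lacks duration, one lacks the bilirubin cut, the crossing and INR, one lacks the symptom link, and three lack ALP (1 + 1 + 1 + 1 + 3 = 7).

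**Step 2: what the table still gives.**
- If nobody exceeds 5×ULN for ALT or AST, conditions 1 and 2 are exactly zero. If nobody exceeds 3×ULN, conditions 1 to 4 are all zero.
- If nobody exceeds 1.5×ULN for bilirubin, condition 6 and the bilirubin limb of condition 3 are zero.
- Otherwise condition 1 is only bounded. Because ALT and AST are tabulated separately, the count is at least the larger of the two >10×ULN counts and at most the sum of the two >5×ULN counts.

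**Step 3: the lost linkage.** Take two participants. In case A one has ALT 4 and bilirubin 2.5 and the other is normal. In case B one has only ALT 3.1 and the other only bilirubin 1.6. Both cases give one participant in ALT >3 to ≤5 and one in bilirubin >1.5. Condition 3 is met once in A and never in B.

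**Step 4: other planned outputs.** SAP 4.1 includes the maximum in continuous summaries, so the largest ALP and bilirubin at each scheduled visit will be seen. A maximum shows how high the worst value went, not how many participants passed a limit or whether two tests rose together. The treatment-emergent high count puts ALP of 1.1 and 3.5×ULN together. It also excludes anyone above range at baseline, although inclusion criterion 8 admits ALP up to just under 1.5×ULN.

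**Step 5: what a remedy would recover.** With a bilirubin cut at 2×ULN, ALP cuts at 2.5 and 3×ULN and same-sample crossing, conditions 5 and 6 and the bilirubin limb of condition 3 become countable. An either-enzyme cut at 8×ULN adds condition 1, making 3 of 7 plus one limb. Conditions 2, 4 and 7 and the INR limb need dates, symptoms or INR, so they need a listing.

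**The case against.** The strongest case is that no document promises these counts. Protocol 9.4.7 commits only to descriptive laboratory summaries, so the SAP does not contradict the protocol. The 1.5×ULN bilirubin cut also has a rationale: it matches the entry limit and the baseline split in Appendix 7. In a trial of about 80 participants the upper cells may be empty, and then several conditions are known to be zero. Participants taken off drug for a liver event have extra hepatic data collected and appear among discontinuations due to adverse events. Clinically relevant laboratory changes are recorded as adverse events under protocol 8.2.4.

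Most of this stands, and it limits the point. It does not remove it: the zeros depend on results not yet seen, and the adverse-event route counts investigator judgements rather than participants who crossed a threshold.

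A reader might also infer stronger things that the documents do not support:
- That no condition could ever be counted. Step 2 shows otherwise when the upper cells are empty.
- That the SAP ignores ALP. ALP is missing from the category table only.
- That a stopping rule goes unmonitored. The seven conditions prompt consultation, and monitoring runs through protocol 7.1.2 and Appendix 7, independently of these tables.
- That a plot of peak ALT/AST against peak bilirubin would be enough. Peaks may fall on different dates, and such a plot shows neither duration, symptoms nor INR.

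**Conclusion.** The point holds as a gap in safety reporting. When the relevant upper cells are occupied, the shift table fixes the count for none of the seven conditions in protocol 7.1.2, and the generic chemistry summaries do not supply it. Joint elevation of ALT/AST and bilirubin is not shown under any result, unless the single-test cells are empty and so exclude it.

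This rests on reading the third condition as in the working and on the SAP's stated outputs being complete for liver tests. The documents give no expected rate of liver abnormalities, so how often the gap would matter cannot be quantified. The primary efficacy analysis is not touched. The change is worth making because it is cheap and settles what the report can say about liver safety.

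**What to change.** Before unblinding, revise SAP 4.6.3 using the protocol's own thresholds for reporting:

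- **Categories.** Add a bilirubin cut at 2×ULN, an ALT/AST cut at 8×ULN (with a row for either enzyme) and ALP cuts at 2.5 and 3×ULN.
- **Joint counts by arm.** Count ALT or AST above 3×ULN with bilirubin above 2×ULN, and ALP above 2.5×ULN with bilirubin above 2×ULN. Use values from the same sample or within a stated time window. A peak-versus-peak plot may supplement these counts.
- **Listing.** Show every participant who reaches a laboratory threshold in protocol 7.1.2, with dates, consecutive values including repeats (for the 2-week duration), INR where tested, eosinophils, and concurrent adverse events for the symptom limbs.

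The cost is a few tables and one listing that joins laboratory and adverse-event data. ALT, AST, bilirubin and ALP are in the routine chemistry panel, and eosinophils are in haematology. INR is listed only in the hepatic evaluation of Appendix 7, so that limb can be assessed only where the evaluation was triggered. Protocol 9.4.1 requires an amendment only for changes to a principal feature, so describing this in the SAP and study report should suffice. No clinical rule changes.
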